3.5.3 Presentation of results

[figure not shown]
Number of administrations and number of loading doses will be summarized using descriptive statistics. Analysis of NCOD is described in the efficacy section 4.1.3.

All study drug administration data will be listed. Also, a detailed listing of OCS administration and NCOD will be provided including prednisone equivalent doses with body weight at intake, dates of ICE, CDA, PR, CR, CRmin, CRoff, first relapse and end of study (EoS). NCOD and OCS cumulative dose for the periods of interest will be listed.

Frequency tabulations with percentages will be produced for:

- Number of participants/caregivers receiving the self-administration training (denominator is all participants in SAF)
- Number of training visits received (denominator is number of participants/caregivers receiving training)
- Number of participants/caregivers who were adequately trained and capable to self-administer efgartigimod (denominator is number of participants/caregivers receiving training)
- Number of training visits before being considered capable to selfadminister (denominator is number of participants/caregivers receiving training)
- Number of administrations by administrator (site staff, participant, caregiver, home nurse) and location (at home/onsite) per CRF visit and overall

All CRF information related to IMP self-administration and training will be listed.

4. EFFICACY, PHARMACOKINETIC, PHARMACODYNAMIC AND IMMUNOGENICITY ANALYSES

4.1 EFFICACY AND QUALITY OF LIFE

All efficacy endpoints will be analyzed on the FAS population. The primary endpoint and all 5 key secondary endpoints will also be analyzed on the PP population as sensitivity analysis.

Wherever the stratification factors will be used in the efficacy analyses, the actual values of these will be used and not the ones coming from the randomization. Also, for participants randomized without stratification, i.e., part A participants and Japanese or Chinese Part B participants, these factors will be derived in order to include these participants in the statistical models.

For all references to weeks, analysis visits are considered as described in section 2.2.4, unless specified otherwise. If multiple assessments fall within the same analysis window, only the assessment closest to the target date will be considered unless specified otherwise. Other assessments within this window will only be listed and not considered in the below analyses. Only the time to response endpoint (see section 4.1.4) will be derived using all possible measurements and not only the one closest to the target of the analysis visit. Only visits up to Week 36 analysis visit will be considered defining the different responses. For endpoints 'at week 36', the last non-missing analysis visit assessment from week 32 till week 36 will be used.

All endpoints/estimands defined as an event 'while receiving efgartigimod PH20 SC or placebo' should be handled as follows: treatment discontinuations not due to 'lack of efficacy' (but e.g., due to AE) are still considered as 'while receiving efgartigimod PH20 SC or placebo'.

[figure not shown]
Examples of SAS code for the statistical analysis procedures are provided in appendix 9.3.

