8.1.5. Unscheduled Visits

In case of suspected new lesions as reported by the participant, or other issues requiring site staff intervention, such as notable weight changes, participants should come to the clinic for an unscheduled (UNS) visit for disease assessment. The investigator will decide which assessments to conduct based on the purpose of the unscheduled visit (Table 1). In case of relapse, IGA-BP, BPDAI, and Itch NRS assessments must be performed and participants should return to weekly

on-site visits until CDA is achieved again. At the UNS visits, blood samples for PK will only be collected if IMP is administered.

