2.2.4 Analysis visits

For longitudinal responses, all assessments, including unscheduled assessments, will be allocated to analysis windows as defined below. Tables and listings will present the analysis windows, not the case report form (CRF) visits. Allocation of assessments will be done using their relative day (DY, see section 2.2.3). Visit window limits are the mid-point between the scheduled study days for each visit.

Table 2: Analysis visits (for assessments other than disease status)

	•		1.5	
Phase	Analysis window	Target DY	Lower limit DY	Upper limit DY
Screening	Screening ^[2]	-14	-INF	1
Treatment	Baseline	1	-INF	1[1]
	Week 1	8	1[1]	11
	Week 2	15	12	18
	Week 3	22	19	25
	Week 4	29	26	43
	Week 8	57	44	71
	Week 12	85	72	99

Page 26 of 120

SGS		Statistical	Analysis Plan	
ARGX-113-2009		Final and	Interim Analysis	Final 4.0 of 04NOV2024
	Week 16	113	100	127
	Week 20	141	128	155
	Week 24	169	156	176
	Week 26 ^[2]	183	177	190
	Week 28	197	191	211
	Week 32	225	212	239
	Week 36 ^[2]	253	240	End of treatment phase

1

36

35

End of FU phase

FU Week 7

Follow-up [3] FU Week 3

21

49

Table 3: Analysis visits (for disease status assessments)

Phase	Analysis window	Target DY	Lower limit DY	Upper limit DY
Screening	Screening	-14	-INF	1
Treatment	Baseline	1	-INF	1[1]
	Week 1	8	1[1]	11
	Week 2	15	12	18
	Week 3	22	19	25
	Week 4	29	26	32
	Week 5	36	33	39
	Week 6	43	40	46

	Week X ($X = 7 \text{ to } 34$)	X*7+1	X*7-2	X*7+4

	Week 35	246	243	249
	Week 36 ^[2]	253	250	End of treatment phase
Follow-up [2]	FU Week 3	21	1	35
	FU Week 7	49	36	End of FU phase

[figure not shown]
^[1] An assessment on Day 1 will be attributed to Baseline in case it is before the first administration, to Week 1 otherwise.

^[1] An assessment on Day 1 will be attributed to Baseline in case it is before the first administration, to Week 1 otherwise.

^[2] ECG is only captured at screening, W26, W36, ETD and ESD.

^[3] The start date of the follow-up phase will be used as a reference date for the DY calculation.

^[2] The start date of the follow-up phase will be used as a reference date for the DY calculation.

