4.1.1 Available data

BP Disease status is assessed weekly. Investigators report the participant's best BP disease status in episodes with start and end date (no CDA, CDA, CR while receiving OCS therapy of more than 0.10 mg/kg/day, CR while receiving minimal OCS therapy for less than 8 weeks *or* for at least 8 weeks, CR while being off OCS therapy for less than 8 weeks *or* for at least 8 weeks, PR while receiving OCS therapy, PR while being off OCS therapy for less than 8 weeks *or* for at least 8 weeks, Relapse, Treatment failure). The BP disease status at a visit is derived as the status of the episode during which the visit occurred (and only for visits where it is confirmed that the disease status assessment occurred).

Furthermore, efficacy will be evaluated by assessments of NCOD, IGA-BP, Itch NRS and BPDAI Activity and Total Score.

Quality of life will be measured using ABQOL Questionnaire, DLQI and EQ-5D-5L Scale.

The health impact of glucocorticoid (GC) use will be measured using the Aggregate Improvement Score (AIS) from the GTI, the Cumulative Worsening Score (CWS) from the GTI and the Glucocorticoid Toxicity Index Specific List (GTI-SL).

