4.1.3.1 HANDLING OF INTERCURRENT EVENTS, RESCUE THERAPY AND MISSING DATA

1) Normalized cumulative OCS dose (NCOD, mg/kg/day) over the on IMP treatment period.

Main intercurrent events are defined as follows, and handled in a 'while on treatment' strategy:

• Intercurrent medications (see section 3.4.2): stop calculating cumulative dose after ICE. In case 'immunosuppressants for at least 4 weeks in total' is the ICE, use end of the 4 weeks IC medication as stop for cumulative dose calculation. In case 'tetracyclines for at least 2 weeks in total' is the ICE, use end of the 2 weeks IC medication as stop for cumulative dose calculation. In case 'IV or IM corticosteroids' is the ICE, use the first day of this IC medication as stop for cumulative dose calculation. In case 'very potent TCS for 7 consecutive days or 14 days in total' is the ICE, use the end of the 7 or 14 days IC medication as stop for cumulative dose calculation.

Details on the derivation of intercurrent events are provided in appendix 9.1.

A supplementary analysis for this secondary endpoint will use the 'treatment policy strategy' where the occurrence of the intercurrent event is considered irrelevant: NCOD is calculated regardless of whether or not the intercurrent event occurs.

Rescue therapies will not be considered for the NCOD endpoint since rescue therapies are only permitted after discontinuation of IMP treatment and NCOD calculation is restricted to the on IMP treatment period.

- 2) The proportion of participants that have achieved IGA-BP score of 0 while receiving efgartigimod PH20 SC or placebo and have been off OCS therapy for ≥8 weeks at week 36: the same approach for handling the main ICEs (composite strategy), for the handling of rescue therapies and for handling missing data, as suggested for the primary analysis, will be applied.
- 3) The proportion of participants that have achieved control of disease activity (CDA) while receiving efgartigimod PH20 SC or placebo and remain free of relapse through week 36: the same approach for handling the main ICEs (composite strategy), for the handling of rescue therapies and for handling missing data, as suggested for the primary analysis, will be applied.
- 4) The proportion of participants that have achieved CR while receiving efgartigimod PH20 SC or placebo and while receiving minimal OCS therapy for ≥8 weeks (CRmin) at week 36:

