4.1.5 Fixed-Sequence testing procedure

The fixed-sequence testing procedure will only apply for the analysis of study Part B.

To control the type I error for the primary and secondary endpoints (alpha controlled), the primary efficacy endpoint will be tested at the 5% 2-sided alpha level and will act as gatekeeper for the testing of the key secondary endpoints. The primary endpoint and secondary endpoints will be tested in a strict hierarchical order as per the algorithm of section 1.4.3.2 to control the type I error.

The individual per-endpoint tables will only show unadjusted p-values. A fixed-sequence testing procedure table will be produced. This table will show both unadjusted p-values and p-values adjusted for multiplicity. For a given endpoint, the adjusted-for-multiplicity p-value is calculated as the maximum between its unadjusted p-value and the highest of all unadjusted p-values tested before.

- Primary endpoint: the proportion of participants who are in CR while receiving efgartigimod PH20 SC or placebo and have been off OCS therapy for ≥8 weeks at week 36 using a 'composite strategy' approach
- Secondary endpoints:
 - NCOD using 'while on treatment strategy' approach
 - Proportion of participants achieving IGA-BP score of 0 while receiving efgartigimod PH20 SC or placebo and have been off OCS therapy for ≥8 weeks at week 36 using a 'composite strategy' approach
 - Proportion of participants achieving control of disease activity (CDA) while receiving efgartigimod PH20 SC or placebo and remain free of relapse through week 36 using a 'composite strategy' approach
 - Proportion of participants achieving CR while receiving efgartigimod PH20 SC or placebo and have been receiving minimal OCS therapy for ≥8 weeks at week 36 using a 'composite strategy' approach
 - Change from baseline to week 36 in the 24-hour average Itch NRS score using a 'treatment policy' approach

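### A short relapse that falls between the selected weekly assessments can be missed, so the participant counts as relapse-free in key secondary endpoint 3

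*SAP*

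**What the plan says.** SAP 4.1 sets the general rule for efficacy: where several assessments share a window, "only the assessment closest to the target date will be considered unless specified otherwise". The others are excluded: "Other assessments within this window will only be listed and not considered in the below analyses". One exception is named: "Only the time to response endpoint (see section 4.1.4) will be derived using all possible measurements".

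Unscheduled visits are not discarded. Under SAP 2.2.4, "all assessments, including unscheduled assessments, will be allocated to analysis windows as defined below". They compete with the scheduled visit for selection, and ties go to the later assessment.

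Investigators record disease status as dated episodes (SAP 4.1.1). For analysis by visit, "The BP disease status at a visit is derived as the status of the episode during which the visit occurred".

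Key secondary endpoint 3 is handled in SAP 4.1.3.1 item 3. That item only imports the primary endpoint's rules for intercurrent events, rescue therapy and missing data. It does not say how relapse is ascertained, and neither 4.1.3.2 nor 4.1.5 adds anything. The endpoint belongs to the Part B fixed sequence, in which "the primary efficacy endpoint will be tested at the 5% 2-sided alpha level and will act as gatekeeper".

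Protocol 8.1.5 brings participants to the clinic between scheduled visits: "In case of suspected new lesions as reported by the participant, or other issues requiring site staff intervention". A relapse may therefore first be diagnosed at an unscheduled visit.

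**The concern.** Freedom from relapse through week 36 depends on every day from first CDA onwards. A rule that samples one assessment per week suits an endpoint read at a time point, but it can leave gaps in an endpoint of this kind. If a relapse episode covers no selected assessment, following the SAP as written leaves it out, and a participant with a documented relapse counts as relapse-free.

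The same participant would have a first-relapse date in the listing described in SAP 3.5.3. They might also have an event in time from CDA onset to relapse (SAP 4.1.4 item 9), so two analyses of the same trial could classify one person differently.

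The SAP deals with this kind of problem elsewhere. Item 4 of 4.1.3.1 gives key secondary endpoint 4 a derivation from dated episodes. Appendix 9.1 separates endpoints that run through week 36 from those read at week 36, but only for intercurrent treatments. Item 3 has no equivalent.

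**Working it through.** **Windows.** SAP Table 3 gives week X a target of day 7X+1 and limits 7X−2 to 7X+4. For X = 35 this gives target 246 and limits 243 to 249, as printed. Each window is 7 days wide.

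**Example.** Scheduled visits fall on days 78 (week 11 target) and 85 (week 12 target). A relapse starts and is seen at an unscheduled visit on day 79. The week 11 window is days 75 to 81. Day 78 is at distance 0 and day 79 at distance 1, so day 78 is selected and day 79 is only listed. An episode of 6 days runs from day 79 to day 84 and covers no selected visit, so it is lost. An episode of 7 days reaches day 85 and is captured.

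**All visits on target.** Let the unscheduled visit fall on the day of onset, equally likely on any of the 6 non-visit days. The next scheduled visit is g = 1 to 6 days later. An episode of d days is missed when g ≥ d, so the share missed is (7 − d)/6 for d up to 7 and zero beyond.

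**Visits spread over ±2 days** (the tolerance in Protocol 8.1.3, assumed uniform). The unscheduled visit can now be the closest record. For scheduled offsets 0, −1, +1, −2 and +2 it is selected on 0, 2, 1, 4 and 3 of the 6 possible days. That is 10/30 = 33%. Enumerating all combinations gives the last column.

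| Episode length (days) | Missed, visits on target | Missed, visits ±2 days |
|---|---|---|
| 1 | 100% | 67% |
| 3 | 67% | 43% |
| 5 | 33% | 19% |
| 6 | 17% | 9% |
| 7 | 0% | 3% |
| 8 | 0% | 0.7% |
| 9 or more | 0% | 0% |

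A separate simulation, with the unscheduled visit 0 to 2 days after onset, gave 39%, 20%, 5% and 0% for 3, 5, 7 and 10 days.

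**Weight of one participant.** Part B has about 120 participants randomised 1:1, so about 60 per arm, and 1/60 = 1.7 points. Part A has about 20 per arm, so one participant is 1/20 = 5 points. This matters a little because SAP 1.4.3.2 orders the Part B key secondary endpoints by their Part A interim p-values.

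**After the fix.** If every recorded relapse episode counts, the share missed is 0% at every length.

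**The case against.** A reader might infer that the rule drops relapses seen at unscheduled visits in general. It does not. Such visits are windowed and kept when closest to target, and a relapse still ongoing at the next selected visit is counted there.

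Very short relapses also sit awkwardly with Protocol 4.1.3, which calls lesions that heal within a week transient and treats a picture of only new transient lesions as partial remission. This stands in part. The one-week clause in the relapse definition is worded differently in the two documents: the protocol's plural can be read as covering several lesions, while the SAP's singular points to the single large lesion. The limb on extension of established lesions carries no stated minimum. CDA requires only that healing begins, so a relapse episode could close quickly. Short episodes are less likely, but not excluded.

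Other features limit the count, and these stand:
- A participant is misclassified only if every relapse after CDA is missed.
- A second relapse leads to discontinuation of study drug (Protocol 6.8.3). Rescue therapy, or discontinuation for lack of efficacy, already means non-response.
- For home visits, the investigator asks about new lesions within 48 hours before dosing (Protocol 8.1.4). Unscheduled visits prompted by that call would tend to fall near a scheduled one.

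A reader might also infer a definite loss of treatment effect. If 30% of placebo and 15% of efgartigimod participants relapsed and 10 to 20% of relapses were lost in each arm, the difference would shrink by 0.10 × 15 = 1.5 to 0.20 × 15 = 3 points. None of those rates is in the documents. At the 4.7% loss simulated for 7-day episodes, the same sum gives 0.7 points. If relapses were shorter on efgartigimod, the bias could run the other way. Nor is any inflation of type I error shown.

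Finally, the two relapse analyses differ by design. Time to relapse is restricted to participants with CDA, ignores main intercurrent events and censors at rescue. SAP 4.1 exempts a time-to-response endpoint without saying whether time to relapse is one, and 4.1.4 does not spell out how the first relapse date is derived. A conflict between the tables is therefore possible, not certain.

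**Conclusion.** The concern holds in a limited form. The stated rule applies to key secondary endpoint 3 and nothing overrides it, so a participant with a documented short relapse can be counted as relapse-free. This is a wrong classification produced by a written rule, not merely an absent detail.

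Exposure is confined to episodes that (a) are first seen at a non-selected assessment and (b) end before the next selected one. With weekly visits kept within ±2 days, no episode of 9 days or longer can be lost. Longer gaps would need a missed visit or a visit without a confirmed status assessment.

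The percentages by episode length assume uniform onset days and uniform visit spread. They show how the rule behaves and do not predict what this trial will see. Any misclassification raises the responder rate of the arm in which it occurs. Its net effect on the comparison cannot be determined from the documents.

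**What to change.** In SAP 4.1.3.1 item 3, state that any relapse episode with a start date after first CDA and up to the week 36 analysis visit, from any scheduled or unscheduled record, makes the participant a non-responder. Add key secondary endpoint 3 to the exceptions in SAP 4.1. State that the same first-relapse date is used for the time-to-relapse endpoints in 4.1.4, and say there how that date is derived.

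The cost is one sentence in item 3 and a matching clause in each of 4.1 and 4.1.4, plus a small programming change. No new data are needed, because dated episodes are already collected. The change should be made before the Part B database is locked and unblinded.

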4.1.1 Available data

BP Disease status is assessed weekly. Investigators report the participant's best BP disease status in episodes with start and end date (no CDA, CDA, CR while receiving OCS therapy of more than 0.10 mg/kg/day, CR while receiving minimal OCS therapy for less than 8 weeks *or* for at least 8 weeks, CR while being off OCS therapy for less than 8 weeks *or* for at least 8 weeks, PR while receiving OCS therapy, PR while being off OCS therapy for less than 8 weeks *or* for at least 8 weeks, Relapse, Treatment failure). The BP disease status at a visit is derived as the status of the episode during which the visit occurred (and only for visits where it is confirmed that the disease status assessment occurred).

Furthermore, efficacy will be evaluated by assessments of NCOD, IGA-BP, Itch NRS and BPDAI Activity and Total Score.

Quality of life will be measured using ABQOL Questionnaire, DLQI and EQ-5D-5L Scale.

The health impact of glucocorticoid (GC) use will be measured using the Aggregate Improvement Score (AIS) from the GTI, the Cumulative Worsening Score (CWS) from the GTI and the Glucocorticoid Toxicity Index Specific List (GTI-SL).

4.1.2 Primary Endpoint

[figure not shown]
4.1.2.1 ESTIMAND ANALYSIS

- Population: adult participants with newly diagnosed or relapsing BP, regardless of whether the participant is naïve to treatment or has previously received treatment. Participants will be receiving concurrent therapy of oral prednisone (or equivalent OCS); therefore, candidates who have a known contraindication to OCS will be excluded from study participation (exclusion criterion 4).
- Subject level variable: being in CR while receiving efgartigimod PH20 SC or placebo and have been off OCS therapy for ≥8 weeks (CRoff) at week 36.
- Main intercurrent events:
 - 1. Intercurrent treatments before week 36 (see appendix 9.1)
 - Immunosuppressants or dapsone at therapeutic doses for at least 4 weeks in total
 - IVIg /SCIg at immunomodulating dose (≥1 g/kg/month)
 - Tetracyclines at therapeutic dose for at least 2 weeks in total
 - Rituximab or other anti-CD20 biologics, at least 1 infusion
 - Plasma exchange or Immunoadsorption, at least 1 procedure
 - IV or IM corticosteroids

At least 1 administration, any dose, from week 28 to 36 (i.e., during the 8-week period required to confirm CR off OCS therapy) or

At any time before week 28 in any of the 3 following situations:

- More than 60 mg/day of prednisone or prednisone equivalent dose for 3 consecutive days
- More than 40 mg/day of prednisone or prednisone equivalent dose for 4 consecutive days
- More than 7 days in total

- Any interventional study drugs under development for BP
- Very potent TCS for 7 consecutive days or 14 days in total
- 2. Discontinuation of IMP before week 36 due to lack of efficacy
- 3. Death before week 36

Details on the derivation of intercurrent treatments are provided in appendix 9.1.

Population-level summary: the odds ratio (with 95% confidence interval [CI])
under efgartigimod PH20 SC in combination with concurrent OCS therapy
versus PBO PH20 SC in combination with concurrent OCS therapy.

4.1.2.2 HANDLING OF INTERCURRENT EVENTS, RESCUE THERAPY AND MISSING DATA

A composite strategy approach will be taken to address all main ICEs. This implies that participants who take intercurrent treatments, participants who discontinue IMP due to lack of efficacy and participants who died before week 36 will be considered non-responders for the primary endpoint analysis.

Participants who receive rescue therapy before Week 36 will be considered non-responders for the primary endpoint analysis.

Missing values will be imputed as follows:

- Missing data for reason of one of the main ICEs will be handled as described above.
- For response 'at week 36', the last non-missing analysis visit assessment from week 32 till week 36 will be used. If all disease status assessments at the analysis windows for week 32 to week 36 are missing, then the participant is considered non-responder.
- Otherwise, if disease status information is missing for the primary endpoint, the participant will be considered a non-responder.
- Handling of missing data due to the cut-off for the Part A interim analysis is described in section 1.4.1.2.

A supplementary analysis for this primary analysis on FAS will use the 'treatment policy strategy' where the main intercurrent events are handled differently. The occurrence of the intercurrent event is irrelevant: CRoff as assessed by the investigator is used regardless of whether or not the intercurrent event occurs. Participants who received rescue therapy before Week 36 are still considered as non-responders for this supplementary analysis. Missing data at week 36 will be imputed by means of multiple imputation (fitted separately per treatment group). However, if a participant died before week 36, this is considered a non-responder (composite strategy).

SGS	Statistical Analysis Plan		
ARGX-113-2009	Final and Interim Analysis	Final 4.0 of 04NOV2024	

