- If CR information is missing for the primary endpoint, the participant will be considered a nonresponder. Further details on other imputation techniques for missing CR information will be provided in the SAP.
- Details on handling other missing data will also be provided in the SAP.

Final analysis model: the proportion of participants with BP who are in CR while receiving efgartigimod PH20 SC or placebo and have been off OCS therapy for ≥8 weeks at week 36 will be tested using a Cochran-Mantel-Haenszel (CMH) test stratified for the 2 stratification factors of disease history (newly diagnosed versus relapsing) and disease severity (moderate versus severe). The odds ratio will be provided, along with the 95% CI and 2-sided p-value.

Supplementary analyses: to facilitate interpretation of the estimated treatment effect in the primary analysis, supplementary analyses will be conducted on the supportive estimand where the main ICEs are handled differently (eg, by using the hypothetical or treatment policy strategy instead of composite strategy). Details will be provided in the SAP.

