1.4.1.2 MISSING DATA IMPUTATION

All missing data imputation rules specified in Section 4.1.2.2 for the primary endpoint will be applied. At the IA cutoff time point, some subjects will have not completed the treatment period. As specified in Section 4.1.2.2, absence of data due to premature study termination or a subject failing to perform the disease assessment at week 36 will be handled using the composite strategy (i.e., subject considered as non-responder).

However, for the IA one more imputation rule is required to handle the fact that some subjects will still be ongoing by the time of data cutoff. For ongoing subjects only, a surrogate endpoint will be defined as 'being in CR while receiving efgartigimod PH20 SC or placebo and is off OCS therapy for ≥8 weeks at last visit'. Derivation of this endpoint follows the same rules and strategies planned in Section 4.1.2.2for the primary endpoint but replacing 'week 36' by 'week X' which will represent subject's last visit before cutoff time point.

For ongoing subjects, the above surrogate endpoint will be used as a proxy (substitute) of the primary endpoint at the IA.

Also, for key secondary endpoints with evaluation at week 36, a surrogate endpoint will be used replacing 'week 36' by 'week X' which will represent subject's last visit before cutoff time point.

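### SAP 4.1.2.2 and SAP 1.4.1.2 classify the same early leaver in opposite ways, and for Part B the week 32–36 look-back is an unlisted, untested departure from the protocol default

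*SAP*

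**What the plan says.** **SAP 4.1 and 4.1.2.2.** Section 4.1 sets the general rule: "For endpoints 'at week 36', the last non-missing analysis visit assessment from week 32 till week 36 will be used". Section 4.1.2.2 repeats it for the primary endpoint ("the last non-missing analysis visit assessment from week 32 till week 36 will be used") and limits imputed non-response: "If all disease status assessments at the analysis windows for week 32 to week 36 are missing, then the participant is considered non-responder". A further bullet makes any other missing disease status a non-response. Intercurrent treatment, IMP discontinuation for lack of efficacy, death and rescue therapy before week 36 all give non-response. Under 4.1, stopping IMP for another reason, such as an adverse event, still counts as receiving it.

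**SAP 1.4.1.2 (Part A interim).** This section first adopts all the imputation rules of 4.1.2.2. It then says, naming 4.1.2.2 as its source, that "absence of data due to premature study termination or a subject failing to perform the disease assessment at week 36 will be handled" by the composite strategy, as non-response.

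**Protocol 9.3.2.** "If CR information is missing for the primary endpoint, the participant will be considered a nonresponder". The next sentence leaves details of other imputation techniques to the SAP.

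**SAP 4.1.3.1.** Key secondary endpoints 2, 3 and 4 take over the primary endpoint's missing-data approach. For number 3 the wording is "remain free of relapse through week 36: the same approach for handling the main ICEs (composite strategy), for the handling of rescue therapies", and missing data are included.

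**SAP 6.1.** The listed changes from the protocol are the body weight used for NCOD, the intercurrent-medication definitions, and death as an intercurrent event. The look-back is not among them.

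**The concern.** SAP 1.4.1.2 attributes to 4.1.2.2 a rule that 4.1.2.2 does not contain, so a programmer cannot follow both. The interim cut-off falls when the last Part A participant reaches week 26. Earlier enrollees may by then have left the study shortly before week 36, or passed it. They are no longer ongoing, so the surrogate endpoint for ongoing participants does not apply to them and the conflicting sentence does. The interim result feeds the futility recommendation and the Part B sample size.

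For the final analysis, the look-back credits success to people whose state at week 36 is unknown. Responder status also requires no intercurrent treatment and no rescue therapy up to week 36, including no IV or IM corticosteroid from week 28 on. None of this is observed after withdrawal. Protocol 4.2.4.1 itself notes that many patients in remission relapse within months.

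No planned analysis shows whether the choice matters. The per-protocol and exact logistic analyses use the same derived response. The treatment-policy analysis is described as multiple imputation, but the SAP's SAS-code appendix (9.3) first carries values missing after week 32 forward.

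**Working it through.** **The rules side by side.** No participant below has a main intercurrent event or rescue therapy.

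| Participant | SAP 4.1 / 4.1.2.2 | SAP 1.4.1.2 | Protocol 9.3.2 default |
|---|---|---|---|
| CRoff at week 32, withdraws in week 33 | Responder | Non-responder | Nonresponder |
| CRoff at week 35, stays in study, misses week 36 | Responder | Non-responder | Nonresponder |
| No assessment in weeks 32–36 | Non-responder | Non-responder | Nonresponder |
| Leaves for lack of efficacy, or dies | Non-responder | Non-responder | Nonresponder |

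The rules diverge only in the first two rows.

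**Age of the carried value.** In SAP Table 3 the disease-status window for week X is day 7X−2 to 7X+4. Week 32 is therefore days 222–228, and the week-36 target is day 253. The carried status is at most 253−222 = 31 days old. For IGA-BP (SAP Table 2) the week-32 window opens on day 212, so the formal maximum is 253−212 = 41 days. With the ±2-day visit window around day 225, the realistic maximum is 253−223 = 30 days.

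**Weight of one participant.** In Part B, 1/60 = 1.7 points. In Part A, 1/20 = 5 points, against futility reference values of 10% and 30%. The futility rule uses confidence limits, so 5 points is the shift in the raw difference. The sample-size step (SAP 1.4.2.1) uses the raw proportions directly.

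**Effect on the Part A sample-size input (illustration).** Per arm, n = [1.960·√(2p̄(1−p̄)) + 1.282·√(p₁(1−p₁)+p₂(1−p₂))]² / (p₁−p₂)².
- 10/20 vs 4/20 (50% vs 20%): (1.322+0.821)²/0.30² = 51.01, so 52 per arm and 104 in total. The planned 120 stands.
- 9/20 vs 4/20 (45% vs 20%): (1.298+0.818)²/0.25² = 71.7, so 72 per arm and 144 in total. An increase above 120 comes into play.

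**Effect on Part B power.** Protocol 9.5 claims more than 90% power with 120 participants; its rates are redacted. At the 20% and 50% used for the simulations in SAP 1.4.2.1, with 60 per arm and two-sided 5%:

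Power = Φ{[0.30 − 1.96·√(2·0.35·0.65/60)] / √[(0.16+0.25)/60]} = Φ{(0.30−0.1707)/0.0827} = 94.1%.

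This agrees with the protocol's claim. The documents give no rate of leaving between weeks 32 and 36. Let L be the share of would-be responders who leave then while in CRoff, assumed to be 0 to 10%. Taking 94.1% as power under the look-back, power under the nonresponder rule is:

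| L | Both arms | Efgartigimod only | Placebo only |
|---|---|---|---|
| 2% | 93.4% | 92.7% | 94.7% |
| 5% | 92.2% | 90.0% | 95.6% |
| 10% | 90.0% | 84.1% | 96.8% |

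**One participant at the boundary (unstratified pooled z-test).** 22/60 vs 12/60 gives p = 0.043; 21/60 vs 12/60 gives p = 0.066. Near the assumed effect nothing turns on one person: 30/60 vs 12/60 gives p = 0.0006, and 29/60 vs 12/60 gives p = 0.0011.

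**The case against.** The strongest reply is that the look-back is deliberate. SAP 4.1, SAP 4.1.2.2 and the LOCF step in the appendix agree, while 1.4.1.2 sits under the interim analysis and begins by adopting all of 4.1.2.2. On that view, all that is wrong is one mistaken paraphrase. This stands for the Part B primary analysis. A reader might infer that the Part B results depend on which SAP section is programmed; the documents do not support that. The internal conflict matters at the Part A interim.

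A reader might also infer that the look-back breaches the protocol. It does not: Protocol 9.3.2 leaves further imputation techniques to the SAP, and 4.1.2.2 keeps non-response as the fallback. It is a departure from the stated default that 6.1 does not list.

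Nor do the documents show that key secondary 3 is certainly carried forward. The look-back is worded for endpoints at week 36, this endpoint runs through week 36, and the SAP's intercurrent-event appendix separates the two classes. But 4.1.3.1 imports the primary approach without saying which part applies, so the text is ambiguous.

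On size, the 41-day gap and the boundary p-values are extremes. Disease status is assessed weekly, and withdrawing participants should, if possible, have a discontinuation visit within 7 days of the last dose. The carried value will often be more recent than week 32. None of this answers the lack of a sensitivity analysis.

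**Conclusion.** The point holds in this form. The SAP contradicts itself on participants in CRoff at weeks 32–35 without a week-36 assessment, so a Part A participant can change class between the interim and the final analysis. For Part B the rule is internally consistent but departs from the protocol default without being listed, and no planned analysis varies it.

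The number affected is probably small, perhaps 0 to 3 per arm; this is an assumption. If 2–10% of would-be responders in both arms left in this window, the nonresponder rule would cost 0.7 to about 4 power points, and up to about 10 if only the efgartigimod arm were affected. These figures rest on 50% vs 20% and on the assumed L. The change should be made because it settles how participants are classified, not because it is likely to reverse the result.

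**What to change.** 1. State one rule in SAP 4.1 and 4.1.2.2 and make 1.4.1.2 match it. Preferably, participants whose study participation ended before week 36 without a week-36 assessment are non-responders, which is the protocol default. The week 32–35 look-back then applies only to participants still in the study who missed that assessment. Because 1.4.1.2 now calls this second group non-responders too, its sentence must be rewritten. Define one day cut-off for all endpoints: the week-36 window opens on day 250 for disease status but day 240 for IGA-BP, so a leaver on day 245 could otherwise be handled differently on the two.
2. List the retained look-back in SAP 6.1. Add a sensitivity analysis in which every participant without a week-36 assessment is a non-responder.
3. State that the look-back does not apply to key secondary 3, so that a participant not followed to week 36 is a non-responder.

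The cost is SAP wording, one condition in the derivation and one extra analysis. Response rates may be slightly lower in both arms. Settle the rule before the Part B unblinding. If the Part A interim has already been run, record which rule was programmed.
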